The amygdala appears to be a critical target for oxytocin's effects on social behavior. Oxytocin receptors have been localized to the amygdala of rodents and humans (Boccia et al., 2013; Insel et al., 1992; Veinante et al., 1997). Data from human neuroimaging studies demonstrate that intranasal OT attenuates amygdala responses to both aversive and positive social cues (Domes, Heinrichs, Glascher, et al., 2007; Kirsch et al., 2005; Labuschagne et al., 2010; Petrovic et al., 2008; Riem et al., 2012; Wittfoth-Schardt et al., 2012). While the exact mechanism mediating OT's effect is unclear, it has been hypothesized that OT receptor activation of GABAergic interneurons in the amygdala plays an important role in the inhibitory effects of OT on amygdala responding to social cues (Ehrlich et al., 2009; Huber et al., 2005). Intranasal OT improves fear recognition in healthy controls, findings that are particularly interesting given the deficits in fear processing that have been found in CD subjects (Fischer-Shopty et al., 2010). **Taken together these data suggest that altered amygdala reactivity is a significant factor in the emotional dysregulation associated with cocaine dependence.**

B. INNOVATION

- The proposed project will be the first to use both social evaluative feedback and an uncontrollable cognitive challenge to study stress-related brain activity in cocaine-dependent individuals.
- This is the first clinical investigation of oxytocin on social stress-related brain activity in cocaine-dependent individuals.
- The proposed studies are the first to examine the impact of social stress on brain activity at a network level.
- Drug addiction has typically been modelled as dysregulation in “top-down” control. The use of an implicit facial affect recognition paradigm will allow us to assess addiction as dysregulation in “bottom-up” drive.

C. APPROACH

C1. Research Team

C1a. Overview

We have assembled a multidisciplinary team with unique and complementary skills in addictions research, neuroimaging and clinical studies of oxytocin. The project will be led by [name]. [name]., Ph.D., [name] M.D., [name] and [name] Ph.D. are Co-Investigators (Co-Is) on the project. [name] will oversee the neuroimaging data acquisition and analysis. Drs. [name] and [name] are clinician scientists and will oversee the safety of the research participants. Each of the Co-Is will be involved in data interpretation and manuscript development.

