Figure 2. (A) Areas exhibiting significant task-dependent (stress > control) functional connectivity with the left amygdala during the MIST in the CD group: bilateral posterior cingulate MNI coordinates (+2, -54, 30) Brodmann area (BA 23); and the HC group bilateral OFC (-40, 58, 2) Brodmann area (BA 10). Z statistic images were thresholded using clusters determined by $Z > 2.3$ and a corrected cluster significance of $p < 0.05$ (B) Peak anxiety to the MIST. Values are group means (+) se * Denotes significant difference from HC ($p < 0.05$).

[figure not shown]
the OFC during the stress condition than the control condition. Cocaine-dependent subjects reported significantly greater anxiety in response to the MIST than the HC subjects (Figure 2B). Thus, these preliminary findings support our hypotheses and the feasibility of using PPI to assess functional connectivity associated with a social stress task in CD and HC subjects.

C2b. Oxytocin Attenuates Anxiety in Marijuana-Dependent Individuals

In a double blind placebo controlled study, we investigated the impact of intranasal OT administration on subjective responses to the Trier Social Stress Task in marijuana-dependent individuals. Compared with subjects who received placebo, subjects that received OT reported significantly lower subjective anxiety ($p=0.05$) and drug craving ($p < 0.05$) (McRae-Clark et al., 2013).

C2c. Evidence for Hyperactive Amygdala Responses to Social Stress in CD Subjects

In a pilot study, we used the MIST to compare social stress-related brain activity between CD individuals ($n=13$) and healthy controls (HC; $n=15$). Using a block design BOLD fMRI data were collected during three runs of the MIST. During social stress (stress condition-control condition) CD subjects exhibited significantly greater activity in the left amygdala than HC subjects (Figure 3A). In contrast, during social stress the HC subjects did not exhibit significantly greater activity than the CD subjects in any brain region. During mental arithmetic (control condition-rest condition), the HC subjects exhibited significantly greater activity in the anterior cingulate cortex than the CD subjects (Figure 3B).

C2a. Evidence for Corticolimbic Uncoupling in CD Individuals

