Power and sample size estimates for Hypotheses 1A and 1B were based on pilot data from the MIST (see Preliminary Studies). Based on these data we expect a between group difference (CD-PBO vs. HC-PBO) in the PPI beta estimate of OFC-amygdala connectivity of $\Delta=3.6$ with a RMSE=4.0 ($d = 0.9$) (Cohen, 1988). Assuming an effect similar to the pilot data, the total effective sample size would be 40 subjects per group to provide 80% power for a between groups study design with a type I error rate of 0.05.

Power and sample size estimates for Hypothesis 1C were based on data from a double-blind placebo controlled pilot study of OT on stress reactivity to the Trier Social Stress Task in CD subjects. Based on these data we expect a between group difference in cocaine craving following the MIST of $\Delta=8.24$ with a RMSE=11.03

($d=0.75$) (Cohen, 1988) and a subjective anxiety difference of $\Delta=1.07$ with a $RMSE=2.20$ ($d=0.49$). As in the oxytocin pilot study, participants will be assessed at five time points (m), with an anticipated intraclass correlation coefficient of 0.78 for both craving and anxiety outcomes ($ICC=0.78$ & 0.79, respectively). The design effect, which accounts for the multiple correlated observation within each subject, is estimated to be 4.12 ($DE= [1+(5-1)0.78]$) (Donner and Klar, 2000). Assuming independent observations and an effect similar to the pilot data for the anxiety response ($d=0.48$), the total effective sample size would be 140 subjects (35 CD and 35 controls per treatment arm) to provide 80% power with a type I error rate of 0.05. In a clustered setting, the sample size is $N_{\text{effective}} = nm/DE$ where n is the number of participants required when m replications within participants are performed after accounting for the design effect (DE). For the study at hand, the total number of participants required is therefore estimated to be $N=135$ ($=140*4/4.12$), As such, our proposed sample size of 160 subjects (40 CD and 40 HC per treatment arm) should provide sufficient statistical power to detect the planned anxiety and craving responses to the MIST. To account for an estimated attrition rate of 45%, we will enroll 210 participants in order to complete 160 scans.

Specific Aim 2

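### Power for Hypothesis 1B is borrowed from a cocaine-versus-control contrast with no oxytocin connectivity data behind it, and the stated effect size, sample size and power do not agree

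*Combined protocol and SAP*

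**What the plan says.** The Specific Aim 1 part of Power and Sample Size opens: "Power and sample size estimates for Hypotheses 1A and 1B were based on pilot data from the MIST (see Preliminary Studies"). One effect size follows, and the plan names its contrast: "we expect a between group difference (CD-PBO vs. HC-PBO) in the PPI beta estimate of OFC-amygdala connectivity". Its value is a difference of 3.6 with RMSE 4.0, so d = 0.9. On the premise that the study effect resembles the pilot's, the plan concludes that "the total effective sample size would be 40 subjects per group to provide 80% power". Alpha is set at 0.05, and the plan does not say whether the test is one- or two-sided.

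Statistical Methods assigns an unpaired t-test to each hypothesis: CD-PBO against HC-PBO for 1A, and CD-OT against CD-PBO for 1B. Both are run as second-level FLAME 1 analyses, thresholded at Z > 2.3 with a corrected cluster threshold of 0.05. Participants whose head motion exceeds 0.2 mm are excluded.

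The pilot results in C2a and C2c compare cocaine-dependent with healthy participants and describe no drug administration. Section B adds: "This is the first clinical investigation of oxytocin on social stress-related brain activity in cocaine-dependent individuals". For 1B itself, Specific Aims and Figure 1 state only a direction.

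**The concern.** The section presents one calculation as covering two different questions. 1A asks how far cocaine-dependent participants differ from healthy ones. 1B asks how far a single dose of oxytocin moves cocaine-dependent participants. The first can be estimated from the pilot and the second cannot. Carrying 3.6 units over to 1B sets the oxytocin effect equal to the entire gap between the groups, and the plan neither says so nor argues for it.

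This matters because 1B is the randomised comparison in the connectivity part of Aim 1, and section 5.1 lists connectivity first among the primary outcomes. A reader who accepts the stated 80% could give a null 1B result more weight than it can bear.

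**Working it through.** **Inputs.** From Power and Sample Size, Specific Aim 1: difference 3.6, RMSE 4.0, alpha 0.05, 40 per group, 80% power. From Statistical Methods: unpaired t-test. Assumed: a two-sided test; the pilot RMSE of 4.0 as the SD for CD-OT against CD-PBO; one regional value per participant; all 40 per arm analysed.

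**Step 1: reproduce the plan's figure.** d = 3.6 / 4.0 = 0.90.

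- n per group (normal approximation) = 2 × (1.960 + 0.842)² / d² = 2 × 7.85 / 0.81 = 19.4, so 20. The noncentral t gives 20.4, so 21.
- Power at 40 per group = Φ(d × √(n/2) − 1.960) = Φ(0.90 × 4.472 − 1.960) = Φ(2.065) = 98.1%. The noncentral t gives 97.8%.
- One-sided, the requirement is 16 per group, and 40 per group gives 99%.

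The combination of d = 0.9, 40 per group and 80% power therefore does not reproduce. Forty does match the total for two groups (2 × 20), but the text says per group. Inflating 21 for the plan's 45% attrition gives 21 / 0.55 = 38.2, so 39. That is close to 40, but the plan calls 40 an effective sample size and applies attrition separately, to the 160 scans.

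**Step 2: smallest effect with 80% power at 40 per arm.** d = (1.960 + 0.842) × √(2/40) = 2.802 × 0.2236 = 0.627; the noncentral t gives 0.634. In beta units, 0.634 × 4.0 = 2.5. As a share of the pilot gap, 0.634 / 0.90 = 70%.

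**Step 3: power for 1B by share of the gap that oxytocin closes.** The shares are an assumed range; the documents give none.

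| Share of 3.6 | d | Power at 40 per arm (t) | Power (normal) | n per arm for 80% (normal) |
|---|---|---|---|---|
| 100% | 0.90 | 97.8% | 98.1% | 20 |
| 80% | 0.72 | 88.9% | 89.6% | 31 |
| 70% | 0.63 | 79.5% | 80.4% | 40 |
| 60% | 0.54 | 66.5% | 67.5% | 54 |
| 50% | 0.45 | 51.1% | 52.1% | 78 |
| 33% | 0.30 | 25.9% | 26.4% | 178 |
| 25% | 0.225 | 16.9% | 17.0% | 311 |

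**Step 4: precision of the pilot effect.** C2c gives 13 cocaine-dependent and 15 healthy participants for the activation analysis. C2a gives no number for the connectivity analysis. If the numbers were the same, SE(d) = √(1/13 + 1/15 + 0.81/56) = 0.398, and the approximate 95% interval is 0.90 ± 1.96 × 0.398 = 0.12 to 1.68.

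**Step 5: the oxytocin effects the plan does report.** The Hypothesis 1C calculation uses an oxytocin pilot in cocaine-dependent participants: craving 8.24 / 11.03 = 0.75 and anxiety 1.07 / 2.20 = 0.49. Effects of those sizes would have about 91% and 57% power at 40 per arm. They concern subjective ratings, so they are only a rough guide to connectivity.

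**The case against.** The best defence is that the planned sample is more generous than the text says. A reader might infer that the 80% for 1B holds only if oxytocin closes the whole gap. The documents do not support that. Full closure would give about 98%, and 80% power survives an oxytocin effect about 30% smaller than the pilot gap. The stronger claim would need about 20 per group, which is not the plan. Nor does the plan claim that oxytocin normalises connectivity: Figure 1 states only that CD-OT exceeds CD-PBO. Full closure is what reusing the number implies, not something the authors assert.

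A reader might also infer that the investigators have no oxytocin pilot data. They do: the 1C calculation rests on a placebo-controlled oxytocin pilot in this population. What is missing from the available text is an oxytocin effect on connectivity. Part of the document just before the pilot results was not available for this review, so further pilot detail cannot be excluded.

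The RMSE of 4.0 comes from the same task and outcome, and is a reasonable variance input for 1B. Only the difference is borrowed. It is also fair to say that the power figures above are for a single-region t-test, not the whole-brain test in the plan, and that nothing in the documents says how a null 1B would be interpreted.

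All of this stands, and it limits the claim. It supplies neither an effect size for 1B nor agreement between the stated d, n and power.

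**Conclusion.** The point holds in two parts. First, the effect size used for 1B belongs to 1A. Applied to 1B it equates the oxytocin effect with the full 3.6-unit gap, without a stated reason or supporting connectivity data in the available text. Second, the stated figures disagree: d = 0.9 needs about 21 per group for 80% power, and 40 per group gives about 98%.

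For 1B, 40 analysed per arm give 80% power at d = 0.63 (about 2.5 units, about 70% of the gap), about 51% at half the gap and about 26% at a third. Whether 1B is underpowered cannot be settled from the documents, because the true oxytocin effect is unknown.

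The figures assume a two-sided 0.05 test, SD 4.0 and one regional value. Actual power is likely to be lower. The planned test is cluster-corrected across the brain, and motion exclusions will reduce the number analysed, whereas the 160 in the plan counts completed scans. The interval for the pilot d further assumes that the connectivity analysis used the 13 and 15 participants of the activation analysis.

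**What to change.** Split the Aim 1 power statement. Keep d = 0.9 for 1A only, and restate its power at 40 per group as about 98% (two-sided 0.05, single-region comparison). For 1B, insert:

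> No pilot estimate of the oxytocin effect on amygdala-OFC connectivity is available. Assuming SD 4.0, two-sided 0.05 and a single-region comparison with 40 analysed per arm, power is 80% for d = 0.63 (about 2.5 units, about 70% of the pilot CD-HC difference) and about 51% for half that difference. Power for the cluster-corrected whole-brain test, or after motion exclusions, is likely to be lower.

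If the investigators do hold oxytocin connectivity data, the first sentence should give that estimate instead.

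Also report the CD-OT minus CD-PBO difference in extracted OFC PPI beta with its 95% confidence interval, so that a null result can be read against the 3.6-unit gap. Statistical Methods does not specify this extraction for 1B, so the OFC region must be defined in advance.

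The cost is a change of wording and one small added analysis. Sample size, treatment and procedures are unchanged. The downside is a less favourable stated power for 1B.

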Preprocessing: Post-acquisition preprocessing and statistical analysis of all of the neuroimaging data will be performed using FEAT (FMRI Expert Analysis Tool) Version 5.98, part of FSL (FMRIB's Software Library, www.fmrib.ox.ac.uk/fsl). Functional magnetic resonance imaging (fMRI) blood oxygen level dependent (BOLD) imaging data will be acquired using a standard multi-slice gradient echo planar imaging sequence (TR=2200 ms, TE=35 ms, 64 x 64 matrix, 3 mm isotropic voxels, 271 volumes). Data will be preprocessed using scripting tools from FMRI Expert Analysis Tool (FEAT) Version 5.98, part of FMRIB's Software Library (FSL; www.fmrib.ox.ac.uk/fsl). First non-brain signal will be removed using FSL's BET brain extraction. Scans will be corrected for motion using FSL's linear registration and scans will be spatially smoothed using a Gaussian kernel of 8 mm FWHM. Since head motion can impact functional connectivity analyses, participants with head motion exceeding 0.2 mm will be excluded from the analyses (Power et al., 2012). The "fsl_motion_correction" scripting tool will be used to identify and scrub motion artifacts from each participant's data (Power et al., 2013). Scans will be spatially co-registered with a standardized anatomical template (Montreal Neurological Institute) using a 12 parameter affine transformation (Rorden et al., 2000). **Analysis:** Functional connectivity will be measured using a PPI based approach (Friston et al., 1997). A customized square wave form representing the task (1 = stress condition and -1 = control condition) and the duration of each condition will be convolved with a double-gamma hemodynamic response function. A mask of the seed region will be made using a 12-mm diameter sphere located in the center of the left amygdala using the MNI coordinates (x, y, z = -22, 0, -22). The transformation parameters described above will also be applied to the mask. For each participant and each run of the MIST, the mean corrected and high pass filtered time series of the BOLD signal in the left amygdala will be extracted and used in a single subject whole brain PPI analysis. The PPI model will include (1) the task vector; (2) the time series of the BOLD signal in the left amygdala; (3) a term representing the positive task x seed interaction; and (4) a term representing the negative task x seed interaction. The first level analysis will generate contrast images of the parameter estimates for each of the four regressors. Since the hypotheses associated with Specific Aim 1 explore increases in amygdala - prefrontal cortical connectivity in response to social stress, the group analysis will focus on the positive interaction term. The contrast images of the parameter estimates of the positive interaction term will be entered into a 2nd-level random effects analysis. Unpaired t-tests will be used to test for the following group differences (Hypothesis 1A: CD-PBO vs. HC-PBO) and (Hypothesis 1B: CD-OT vs. CD-PBO). Analyses will be conducted using FMRIBs Local Analysis of Mixed Effects (FLAME 1). Additional analyses comparing (HC-OT vs. CD-OT) will be conducted using an unpaired t-test and applying the appropriate corrections for multiple tests. We will also conduct an exploratory gender analysis between the CD and HC women in the four groups (Domes, Heinrichs, Glascher, et al., 2007; Domes et al., 2010; Potenza et al., 2012). We anticipate that 15-20% of the subjects in each group will be female (n=6/8 per group). We

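### The power statement for Hypotheses 1A and 1B does not follow from its inputs: at d = 0.9, 21 per group give 80% power and 40 per group give about 98%, and no effect is given for the 1B contrast

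*Combined protocol and SAP*

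**What the plan says.** Under Power and Sample Size, Specific Aim 1, the plan says: "Power and sample size estimates for Hypotheses 1A and 1B were based on pilot data from the MIST". It then gives the effect: "we expect a between group difference (CD-PBO vs. HC-PBO) in the PPI beta estimate", and puts the figure for "OFC-amygdala connectivity of $\Delta=3.6$ with a RMSE=4.0 ($d = 0.9". The conclusion is that "the total effective sample size would be 40 subjects per group to provide 80% power for a between groups study design". Alpha is set at 0.05, and sidedness is not stated.

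The test is named in C3f, Statistical Methods, Specific Aim 1: "Unpaired t-tests will be used to test for the following group differences", namely CD-PBO vs HC-PBO for 1A and CD-OT vs CD-PBO for 1B. The same section makes this a second-level whole-brain analysis in FLAME 1 with group results thresholded at Z > 2.3 and a corrected cluster p of 0.05. It excludes participants whose head motion exceeds 0.2 mm.

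The final size is "our proposed sample size of 160 subjects (40 CD and 40 HC per treatment arm". Attrition comes after that: "To account for an estimated attrition rate of 45%, we will enroll 210 participants in order to complete 160 scans".

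**The concern.** There are two separate problems in one short paragraph.

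1. **The arithmetic.** Effect, standard deviation, alpha, power and test are all given, so the group size follows from them apart from sidedness. An effect of d = 0.9 is large, and 40 per group is roughly twice what 80% power requires.
2. **The contrast.** The paragraph claims to cover 1A and 1B, but its one effect size is a difference between cocaine-dependent and healthy participants on placebo. Hypothesis 1B asks about oxytocin against placebo within cocaine-dependent participants. A disease difference does not tell us the size of a drug effect.

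This is the only power statement for 1A and 1B, and section 5.1 lists amygdala-prefrontal connectivity first among the primary outcomes. As written, it suggests that 80% power is reached only for effects near 0.9. A null result on either hypothesis would then be read against the wrong benchmark.

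**Working it through.** **Inputs.** Difference 3.6, RMSE 4.0, alpha 0.05 and power 80% come from Power and Sample Size, Specific Aim 1. The unpaired t-test comes from C3f, Statistical Methods. Allocation is 40 per cell. Two-sided alpha is my assumption; one-sided is shown as well.

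**Standardised effect.** d = 3.6 / 4.0 = 0.9, as the plan states.

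**Trying to reproduce 40 per group.**

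- Normal approximation: n = 2(1.960 + 0.842)² / 0.9² = 2 × 7.85 / 0.81 = 19.4, so 20 per group.
- Exact noncentral t: n = 20.4, so 21 per group.
- One-sided alpha 0.05, exact t: 15.99, so 16 per group.

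None of these gives 40.

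**Power at given group sizes (d = 0.9, two-sided 0.05).** For 40 per group the noncentrality is 0.9 × √(40/2) = 4.02. By the normal approximation, power is Φ(4.02 − 1.96) = 98.1%.

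| Per group | Exact t | Normal approximation |
|---|---|---|
| 20 | 79.2% | 81.2% |
| 21 | 81.2% | not needed |
| 40 | 97.8% | 98.1% |

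One-sided, 40 per group give 99%.

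**Could another convention explain 40?**

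- Bonferroni alpha of 0.025, 0.0125 or 0.0083 (two-sided, exact t) needs 25, 30 or 32 per group.
- Using Z > 2.3 as a one-sided alpha (0.0107) needs 26 per group.
- For 40 per group to give exactly 80%, two-sided alpha would have to be about 0.0022 (t) or 0.0015 (normal). The plan says 0.05.
- Inflating for 45% attrition gives 21 / 0.55 = 38.2, so 39, which is close. The text excludes it: 40 is called an effective size, 4 × 40 = 160 is the number of completed scans, and attrition is applied afterwards to reach 210.
- Forty as the total for two groups (20 each) gives 79.2% by t or 81.2% by the normal approximation, which matches 80% after rounding.

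**Detectable effect at 40 per group, 80% power, two-sided 0.05.** Normal approximation: d = 2.80 × √(2/40) = 0.63. Exact t: 0.634.

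**Hypothesis 1B.** No oxytocin effect on connectivity is stated. The MIST pilot results in C2a and C2c compare cocaine-dependent with healthy participants. The oxytocin pilot cited for 1C used the Trier task and supplies only craving and anxiety effects. If the true oxytocin effect were d = 0.5, 40 per group would give about 60% power; at d = 0.4, about 42%. Both values are illustrative assumptions, chosen only to show how sensitive 1B is.

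**The case against.** The strongest reply is that nothing in the design turns on this sentence. The argument for 160 participants is made in the 1C paragraph (140, then 135, then 160), and the 1A error runs in the safe direction. That stands, and it limits the point to a correction of the text.

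A second reply is that an unqualified 98% would mislead. It is the power of a single two-group t-test with every scan analysable. The plan's analysis is whole-brain with a cluster threshold, and motion exclusions may bring the analysed number below 40 per group with no stated allowance. The pilot effect is also imprecise. If it came from the 13 cocaine-dependent and 15 healthy participants of C2c, SE(d) ≈ √(1/13 + 1/15 + 0.9²/56) = 0.40, so an approximate 95% interval is 0.12 to 1.68. This stands too, and the corrected wording has to carry the caveats.

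A third reply is that the plan openly assumes an effect similar to the pilot under a heading that covers both hypotheses. That makes 1B an explicit assumption, but not a supported one, because the pilot effect quoted belongs to a different contrast.

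The documents do not support several stronger readings that a reader might infer:

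- **That the trial is oversized and could be cut to 21 per group.** The size is argued from 1C, and the 21 ignores the cluster threshold, motion exclusions and pilot imprecision.
- **That no oxytocin pilot estimate for connectivity exists.** None is quoted, but some text just before the pilot results was not available for review, so its absence cannot be asserted.
- **That the primary imaging outcomes have no other power statement.** Specific Aim 2 has its own (effect 1.2, n = 19, power 0.95).
- **That 40 was certainly a total mislabelled as per group.** The numbers fit, and the wording mixes total with per group, but this is inference.

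**Conclusion.** The stated power is wrong for the stated inputs. At d = 0.9 and two-sided alpha 0.05, 80% power needs 21 per group (16 if one-sided), and 40 per group give about 98%. No variant consistent with the text yields 40 per group at 80%. For 1A the error is conservative: on its own inputs the comparison is not underpowered.

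For 1B, the 80% claim rests on an effect quoted for a different comparison. What can be said without a further assumption about oxytocin is that 40 per group reach 80% power at d = 0.63.

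These figures assume a single unpaired comparison, equal groups of 40 analysable scans and two-sided alpha 0.05. They make no allowance for the cluster-corrected whole-brain analysis or for motion exclusions.

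**What to change.** Replace the 1A/1B sample-size sentence with wording such as:

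> *For a single two-group comparison with 40 analysable scans per group and two-sided alpha 0.05, power is about 98% at the pilot effect d = 0.9 for Hypothesis 1A (21 per group would give 80%). For Hypotheses 1A and 1B, 80% power is reached at d = 0.63. These figures do not allow for the whole-brain cluster threshold or for head-motion exclusions.*

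Then add one sentence giving the basis for the effect assumed under 1B. If there is none, let the detectable effect of d = 0.63 stand as the power statement for 1B. If a one-sided test was intended, say so and restate the figures.

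The cost is one paragraph of protocol text. Enrolment, endpoints and tests do not change.

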
acknowledge that we may be underpowered to conduct these tests. Since there may be important group differences in regional brain activity during the MIST, a secondary whole brain analysis will be conducted using the contrast of interest (stress-control). Analyses will be conducted using FMRIBs Local Analysis of Mixed Effects (FLAME 1). All group level results will be thresholded at $Z>2.3$ using a corrected cluster threshold of $p=0.05$.

Hypothesis 1C: The CD-OT group will report lower subjective anxiety and craving than the CD-PBO group.

Analysis: A linear mixed effects model containing all serially measured time points will be used to assess the effects of OT versus placebo on each dependent variable. Restricted maximum likelihood (REML; Patterson and Thompson, 1971) methods will be used to estimate the fixed effects and variance components, and baseline values will be used as covariates in the regression models. The dependent variables anxiety and craving will be modeled separately. Within each family of dependent measures, the Type I error rate will be controlled using a post-hoc Bonferroni correction. The statistical analyses will be conducted using SAS 9.3 software (SAS Institute Inc., Cary, NC, USA).

Specific Aim 2: Use an implicit facial affect recognition paradigm to determine the impact of cocaine dependence and oxytocin on amygdala activity in response to fearful faces.

Hypothesis 2A: The CD-PBO group will exhibit greater amygdala activity in response to fearful faces than HC-PBO group.

Hypothesis 2B: Compared with the CD-PBO group, participants in the CD-OT group will exhibit lower amygdala activity in response to fearful faces.

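### The 80% power given for Hypothesis 1C is calculated for 70 oxytocin vs 70 placebo with healthy controls in both arms, and does not apply to the CD-only comparison (40 vs 40) that the hypothesis names

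*Combined protocol and SAP*

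**What the plan says.** Specific Aims and section C3f (Statistical Methods) both state the comparison: "Hypothesis 1C: The CD-OT group will report lower subjective anxiety and craving than the CD-PBO group". Section 5.1 lists anxiety and craving responses to the MIST among the primary outcomes.

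The analysis text in C3f is a linear mixed model that "will be used to assess the effects of OT versus placebo on each dependent variable". It adds that "baseline values will be used as covariates in the regression models" and that "Within each family of dependent measures, the Type I error rate will be controlled using a post-hoc Bonferroni correction". It does not say whether healthy controls enter the model, and it names no group-by-treatment term.

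Power and Sample Size, Specific Aim 1, takes its 1C effect sizes from an oxytocin pilot in CD subjects: craving 8.24 with RMSE 11.03, and anxiety 1.07 with RMSE 2.20. It assumes five time points, "with an anticipated intraclass correlation coefficient of 0.78 for both craving and anxiety outcomes", and a design effect of 4.12. At d = 0.48, "the total effective sample size would be 140 subjects (35 CD and 35 controls per treatment arm) to provide 80% power". It then says "the total number of participants required is therefore estimated to be $N=135$ ($=140*4/4.12"), and concludes that 160 participants, 40 CD and 40 HC per treatment arm, "should provide sufficient statistical power to detect the planned anxiety and craving responses to the MIST".

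**The concern.** The hypothesis is about CD participants, and so is the pilot effect. The sample size that delivers 80% power is twice the number of CD participants it contains, because healthy controls supply the other half. No pooled analysis is described that would let those controls count, and no oxytocin effect in controls is given.

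A null anxiety result would then be read against a power figure that belongs to a different comparison. The RMSE behind both effect sizes is also undefined, so a reader cannot work out the correct figure from the plan.

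**Working it through.** **Inputs** (Power and Sample Size, Specific Aim 1, unless noted). Anxiety d = 1.07/2.20 = 0.486, printed as 0.49 and then 0.48. Craving d = 8.24/11.03 = 0.747. ICC 0.78. Alpha 0.05, sidedness not stated. Planned 40 CD per arm. Baseline as covariate (C3f).

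**1. The plan's own figure.** Two-sample t-test with n per arm: noncentrality d√(n/2), df 2n − 2.
- d = 0.48, n = 70: 0.48 × √35 = 2.84, power 80.5%. So 140 is the total for 70 vs 70, two-sided. A one-sided test needs 55 per arm (110 in total) and does not match.
- The 35 vs 35 CD inside that total: 0.48 × √17.5 = 2.01, power 50.8%.

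**2. The named comparison, 40 vs 40**, with the RMSE taken as the SD that defines d and no baseline credit.
- Anxiety: 0.486 × √20 = 2.18, power 57.5% (56.4% at d = 0.48).
- Craving: 0.747 × √20 = 3.34, power 91.0%.

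**3. With the plan's formula N_effective = nm/DE**, where DE = 1 + (m − 1) × 0.78:

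| m | DE | Effective n per arm | Anxiety | Craving |
|---|---|---|---|---|
| 3 | 2.56 | 46.9 | 64.4% | 94.7% |
| 4 | 3.34 | 47.9 | 65.4% | 95.1% |
| 5 | 4.12 | 48.5 | 66.0% | 95.4% |

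**4. What the RMSE might be** (assumptions, 40 per arm). Let V = (1 + (m − 1) × 0.78)/m − r², with r the baseline correlation, and replace d by d/√V. If the RMSE is a within-subject residual, the total variance is RMSE²/(1 − 0.78), so V is divided by 0.22. With the covariate, df = 77.

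| Reading of RMSE | V at m = 1, 3, 4 | Anxiety | Craving |
|---|---|---|---|
| Total SD, r = 0.78 | 0.392, 0.245, 0.227 | 93.0%, 99.1%, 99.5% | over 99% |
| Within-subject residual, r = 0.78 | 1.780, 1.113, 1.030 | 36.3%, 53.0%, 56.2% | 69.6%, 87.8%, 90.2% |
| Within-subject residual, no baseline credit | 4.545, 3.879, 3.795 | 17.2%, 19.4%, 19.7% | 34.0%, 38.8%, 39.5% |

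If the RMSE is already baseline-adjusted and the ICC is on the same scale, steps 2 and 3 stand. On the total-SD reading, 80% for anxiety needs r of about 0.64 with one rating or 0.50 with four.

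**5. Alpha.** If the Bonferroni correction means 0.025 (an assumption, as the families are not defined), anxiety is 46% to 55% on the basis of steps 2 and 3, and 88% to 99% on the total-SD reading.

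**6. The printed sample-size step.** 140 × 4/4.12 = 135.9 inverts the plan's formula and mixes four ratings with a design effect built on five. Rearranged correctly, n = N_effective × DE/m: 140 × 4.12/5 = 115.4, or 140 × 3.34/4 = 116.9. The slip is conservative and does not cause the gap.

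**7. If pooling was meant, 80 vs 80.** With the HC effect equal to, half of, or none of the CD effect (an assumed range), the average d is 0.486, 0.365 or 0.243, and power is 86%, 63% or 33%.

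**The case against.** The strongest reply is baseline adjustment. The plan prespecifies it, and the plan's formula is most coherent if the RMSE is the total SD of one rating. If the ICC of 0.78 also covers the pre-treatment rating, the baseline correlation is 0.78 and anxiety power at 40 vs 40 is 93% or more. That stands as a possibility, and it is why a shortfall cannot be asserted. But the power paragraph gives no baseline correlation, does not define the RMSE and claims no such gain.

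The second reply is that pooling was intended. The power paragraph places controls in each arm, the analysis text says oxytocin versus placebo without restriction, and the background promises to explore oxytocin's relation to anxiety and craving in both populations. On that view 1C is loosely worded and the power figure is sound. This too is possible, but it needs the CD pilot effect to hold in controls. The protocol's own background (Oxytocin Modulates Social Behavior) reports mixed findings there: an anxiolytic effect in some studies of healthy controls, none in others.

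The RMSE ambiguity also cuts both ways: craving's 11.03 is as undefined as anxiety's 2.20, so the comfortable craving figures are no less conditional.

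**Conclusion.** The stated 80% power is not shown for the comparison that Hypothesis 1C names. That conclusion needs only the plan's text and one reproduced calculation, and it is firm.

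The size is conditional. On the basis of working steps 2 and 3, anxiety falls short of 80% and craving does not. A reader might infer from this that the trial is underpowered for anxiety, or conversely that craving is safe. The documents support neither as an unconditional statement, because the answer turns on undefined inputs: RMSE, the scale of the ICC, baseline correlation and alpha.

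This should be fixed as a power statement that is wrong as written. It is not evidence that the sample is too small.

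**What to change.** Rewrite the 1C power paragraph for CD-OT vs CD-PBO at 40 per arm, for anxiety and craving separately:
- State whether each RMSE is a total SD, a baseline-adjusted residual or a within-subject residual, and whether the ICC is on the same scale.
- State the assumed baseline correlation.
- Use one d per outcome and one m, with baseline excluded from the outcomes. The rating schedules first need reconciling: C3a lists baseline plus three ratings, while the Within Session Rating Scale entry in C3e lists five, including one before treatment.
- Say whether the Bonferroni correction changes alpha.
- Apply n = N_effective × DE/m and show the inputs.
- Remove the 80% claim for anxiety unless the recalculation supports it. Do not substitute a single figure before the RMSE is defined.

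If pooling over CD and HC was intended, reword 1C and the model to say so, and state the assumption that the CD effect holds in controls.

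The cost is a check of the pilot output and one rewritten paragraph, plus a sentence each in 1C and the model if pooling was meant. Enrolment and endpoints do not change.
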